5.8 Subgroup Analyses

Two subgroups will be examined for the secondary efficacy endpoints:

- Body Weight ($\geq 65\text{kg}$ and $< 65\text{kg}$)
- Sex (male and female).

The analysis of secondary efficacy endpoints (Section 5.4.1.2.1 through to Section 5.4.1.2.4) will be stratified by baseline weight category and sex. If $\geq 95\%$ of study participants fall into one level of any subgroup, then the corresponding summary for that subgroup will not be presented.

5.9 Interim Analyses

There will be no formal interim analysis in this open-label study.

All available study PK data and clinical data (including selected efficacy and safety data) starting from when 25% of participants have reached Week 16 will be assessed periodically until all participants have completed the Initial Treatment Period. The Phase 3 study (PS0021) dosing will be determined from this information.

The PK interim analyses will be conducted when 25%, 50%, 75%, and 100% participants reached Week 16 with PK data available for analysis. The ADA b analyses will be conducted when all participants have completed their Baseline visit and Week 16 visits. A final analysis for PK and ADA b will be conducted at the end of the study including SFU.

The PK interim analysis will include selected efficacy endpoints for relationship between the bimekizumab plasma concentration and the efficacy.

5.10 DMC or Other Review Board

An independent DMC will review and monitor safety data from this study and advise UCB periodically. Further details are provided in a separate DMC charter and DMC SAP. The DMC analysis will be a subset of the analysis outlined in this SAP.

6 SUPPORTING DOCUMENTATION

6.1 Appendix 1: Non-key Analysis Specifications

6.1.1 Baseline characteristics and demographics

Baseline and demographic variables will be summarized by dose group (Dose A, Dose B) and overall, in the RS.

6.1.1.1 Demographics

The continuous demographics variables will be summarized using descriptive statistics including

- Age (years)
- Height (cm)
- Weight (kg)
- BMI (kg/m^2) = weight (kg) / height (m)²

The following categorical variables will be summarized using frequency counts and percentages.

- EudraCT age categories:
 - 12 - <18 years
- Gender
- Racial Group
- Ethnicity
- Region
- Country
- Weight category
 - < 65 kg
 - \geq 65 kg
- Height percentiles
 - <5th
 - \geq 5th to <25th
 - \geq 25th to <50th
 - \geq 50th to <75th
 - \geq 75th to <95th
 - \geq 95
- Weight percentiles: use the same percentile as height
- BMI percentiles (refer to Section 6.3)

- <5th (underweight)
- ≥5th to < 85th (normal or healthy weight)
- ≥85th to <90th (overweight)
- ≥90th to <95th (overweight)
- ≥95th to <97th (obese)
- ≥97th (obese)

6.1.1.2 Lifestyles

Lifestyle variables including alcohol use and smoking will be summarized for the RS. The continuous variables will be summarized descriptively, and the categorical variables will be reported for their frequencies and percentages. Missing values will be reported but not imputed.

6.1.1.3 Other baseline characteristics

Baseline characteristics will be summarized by dose group (Dose A, Dose B) and overall including but not limited to:

- PSO history parameters including duration of psoriasis disease, calculated as [date of randomization – date of PSO first diagnosis] / 365.25, psoriasis present and active at screening, physician's assessment of psoriasis severity, family history of psoriasis, received any prior psoriasis therapy
- Fungal skin infections, including any fungal skin infections in the past 12 months, and any required treatment for fungal skin infections
- Uveitis, including history and duration of uveitis
- IBD, including history and diagnosis
- Psoriatic arthritis, including history and duration of disease
- PSO BSA (%)
- PASI score
- CDLQI total score
- Duration of disease (<median, ≥median)
- IGA score
- Scalp IGA score
- Scalp involvement (yes, no)

The following will be summarized in a past psoriasis treatment and biologic treatment discontinuation reason summary:

- Prior biological treatments (yes, no)
- Prior phototherapy or chemotherapy (yes, no)
- Any prior systemic therapy (yes, no)

Baseline scalp involvement is based on the number of participants achieving scalp IGA>0.

If the date of onset of plaque PSO is partial, it should be imputed to the most recent feasible date (ie, last day of the month if only day is missing, or the last day of the year if day and month are missing). If the date of randomization is missing, then the duration of disease will be derived using the date of Screening. The same algorithm will be applied to duration of uveitis, duration of IBD, and duration of psoriatic arthritis.

Continuous variables will be summarized descriptively. Categorical variables will be summarized using frequency counts and percentages.

6.1.2 Protocol deviations

The number and percentages of participants with important protocol deviations (including a summary of participants excluded from the PK-PPS due to important protocol deviations) will be summarized in the enrolled set by dose group and overall.

A by-participant listing of protocol deviations will be provided.

Important PDs and the PDs that will result in the removal of participants from the PK-PPS are specified in the Protocol Deviation Assessment Plan.

6.1.3 Medical history

Previous and ongoing medical history will be summarized by dose group for the RS by SOC and PT using MedDRA. Medical procedures are not coded and will be listed only.

6.1.4 Prior/concomitant/follow-up medications

Prior medications include any medications that started prior to the start date of study medication. Concomitant medications are medications taken at least one day in common with the study medication or with a start date greater than the last dose of study medication + 28 days. Any medication that started prior to the first dose of IMP and continued after will be classified as both prior and concomitant. Such medications will therefore be counted in the tabulations for both prior and concomitant medication.

The number and percentage of participants taking concomitant medications will be summarized by Anatomical Therapeutic Chemical (ATC) class for each dose group and overall, in the SS. Prior medications and prior antibiotic medications will be summarized similarly.

A by-study participant listing of all concomitant medications will be provided.

Concomitant medications will also be summarized for the Initial Treatment Period, OLE Period, and the combined periods. If participants have duplicate concomitant medication entries with the same date and time, the data will be listed with a flag to identify duplicates. Tables will count duplicates once, but listings will contain all occurrences.

6.1.4.1 Vaccines

Administration of inactivated vaccines and other types of non-live or non-attenuated vaccines is permissible during the study at the discretion of the Investigator and/or following discussion with the Medical Monitor. A prior vaccine refers to a vaccine administered to a participant within the 8 weeks prior to the start date of study medication, and a concomitant vaccine refers to a vaccine

administered with at least one day in common with the study medication dosing period. The vaccine data will be listed.

6.1.5 Past treatments for PSO

Past PSO medications will be summarized by treatment type and reported for each dose group and overall, in the RS. Note that past treatments are collected independently from the prior and concomitant medication data.

6.1.6 Data derivation rules

6.1.6.1 PASI

The PASI scoring of psoriatic plaques is based on 3 criteria: redness (R), thickness (T), and scaliness (S). Severity is rated for each index (R, S, T) on a 0 to 4 scale (0 for no involvement up to 4 for very marked involvement). The body is divided into 4 areas comprising the head (h), upper extremities (u), trunk (t), and lower extremities (l). In each of these areas, the fraction of total surface area affected is graded on a 0-6 scale (0 for no involvement, up to 6 for 90% - 100% involvement).

The various body regions are weighted to reflect their respective proportion of BSA. The composite PASI score is then calculated by multiplying the sum of the individual-severity scores for each area by the weighted area-of-involvement score for that respective area, and then summing the four resulting quantities as follows (note for R, T, and S scores are as follows: 0 = none, 1 = slight, 2 = moderate, 3 = marked, and 4 = very marked):

$$\text{PASI} = (0.1 \times (R_h + T_h + S_h) \times A_h) + (0.2 \times (R_u + T_u + S_u) \times A_u) \\ + (0.3 \times (R_t + T_t + S_t) \times A_t) + (0.4 \times (R_l + T_l + S_l) \times A_l)$$

where

R_h, R_u, R_t, R_l = redness score of plaques on the head, upper extremities, trunk, and lower extremities, scored 0-4 respectively;

T_h, T_u, T_t, T_l = thickness score of plaques on the head, upper extremities, trunk, and lower extremities, scored 0-4 respectively;

S_h, S_u, S_t, S_l = scaliness score of plaques on the head, upper extremities, trunk, and lower extremities, scored 0-4 respectively;

A_h, A_u, A_t, A_l = numerical value translation of % area of psoriatic involvement score for the head, upper extremities, trunk, and lower extremities, respectively (where 0 = 0% [clear], 1 = >0% to <10%, 2 = 10% to <30%, 3 = 30% to <50%, 4 = 50% to <70%, 5 = 70% to <90%, and 6 = 90% to 100%).

The highest potential PASI score is 72 for severe disease; the lowest is 0 for no psoriasis lesions. PASI scores are treated as continuous. The percent improvement in PASI scores from Baseline will be computed as:

$$\text{Percent improvement from Baseline} = 100 \times \frac{\text{Baseline PASI} - \text{Post Baseline PASI}}{\text{Baseline PASI}}$$

If a study participant has experienced an improvement, this measure will be positive. If a study participant has experienced a worsening in their condition, this measure will be negative.

If a study participant is missing 1 or 2 severity measurements for a certain region, the average of the remaining severity measurement(s) within that region will be utilized to substitute for the missing severity measurement(s) in that region. If the area of affected skin and/or all severity measurements for up to 2 regions are missing, then the missing (R+T+S) x A for a region will be substituted by the average of the available (R+T+S) x A. If the area of affected skin and/or all severity measurements for more than 2 regions is missing, but the BSA (Body Surface Area) is reported as 0 for the study participant, then the overall PASI score will be set to 0. Otherwise, the PASI will be set to missing.

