8.1.1 Psoriasis Area and Severity Index

The PASI is the most commonly used and validated assessment for grading the severity of PSO in clinical studies (Feldman, 2004). The PASI quantifies the severity and extent of the disease and weighs these with the percentage of BSA involvement. The PASI will be completed as specified in [Table 1-1](#) and [Table 1-2](#). The PASI will be completed by the Investigator.

The percent area of involvement (BSA%) is estimated across 4 body areas; head, upper extremities, trunk, and lower extremities. Assessors will enter the degree of involvement for a given region on a scale of 0 to 6 (0=none; 1=1% to <10% affected, 2=10% to <30% affected, 3=30% to <50% affected, 4=50% to <70% affected, 5=70% to <90% affected, 6=90% to 100% affected) ([Table 8-1](#)).

The Investigator assesses the average redness, thickness, and scaliness of lesions in each body area (each on a 5-point scale); 0=none, 1=slight, 2=moderate, 3=marked, and 4=very marked.

The PASI score ranges from 0 to 72 with a higher score indicating increased disease severity.

Table 8-1: Body areas for calculation of percent BSA for PASI

Body area	Details of area	BSA	Degree of involvement of body area ^a
Head	Face, back of head	10%	0 to 6
Upper extremities	Left, right, upper lower, flexor surface, extensor surface	20%	0 to 6
Trunk	Front, back, groin	30%	0 to 6
Lower extremities	Left, right, upper lower, flexor surface, extensor surface, including buttocks	40%	0 to 6
Total		100%	

BSA=body surface area; PASI=Psoriasis Area and Severity Index

^a Where 0=none; 1=1% to <10% affected; 2=10% to <30% affected; 3=30% to <50% affected; 4=50% to <70% affected; 5=70% to <90% affected; 6=90% to 100% affected.

The PASI50, PASI75, PASI90, and PASI100 responses are based on at least 50%, 75%, 90%, and 100% improvement in the PASI score, respectively.

The total BSA affected by PSO will be entered as a percentage from 0 to 100.

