	
Clarified that the following will be summarized in a past psoriasis treatment and biologic treatment discontinuation reason summary:
 
 • Prior biological treatments (yes, no) • Prior phototherapy or chemotherapy (yes, no) • Any prior systemic therapy (yes, no) 	Clarification
6.1.4 Prior/concomitant/follow-up medications	Clarified that tables will count duplicates once, but listings will contain all occurrences.	Clarification
6.1.6.1 PASI	Revised derivation to set overall PASI score to 0 when BSA is 0 and the participant is missing area and/or severity measurements for more than 2 regions.	Addition
6.1.6.2 Exposure-adjusted rates	Corrected the formula for LCL and UCL.	Correction; formula was incorrect.
6.1.7.1 Hy's Law	Added the definition for Hy's Law.	Addition
6.1.8.1 Anaphylaxis	Clarified that imputed dates should not be used in the algorithmic approach for anaphylaxis.	Clarification

6.4.2 Amendment 1

Rationale for the amendment

This statistical analysis plan has been amended to modify the endpoints related to vital signs, physical examinations, laboratory analyses, and growth assessments to align with the agreed EU Paediatric Investigation implemented in the protocol amendment 2 dated 15 Mar 2021. In addition, other clarifications, updates to secondary and other endpoints analysis, and specific changes (eg. formats or typos) have been incorporated.

Modifications and changes

Change #1

List of Abbreviations

Added NAb and updated ALT/AST to align with protocol.

Original text:

ALT	serum glutamic-pyruvic transaminase
AST	serum glutamic-oxaloacetic transaminase

Has been changed to:

ALT	alanine aminotransferase
AST	aspartate aminotransferase
NAb	neutralizing antibodies

Change #2

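### SAP 6.1.6.1 does not say that a region with area score 0 contributes 0 to PASI when its severity items are blank, so the missing-item rule could misclassify some PASI90 or PASI75 responders

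*SAP*

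**What the plan says.** SAP 6.1.6.1 builds PASI from four regional products (R+T+S) x A, weighted 0.1, 0.2, 0.3 and 0.4 for head, upper extremities, trunk and lower extremities. An area score of 0 denotes clear skin: "where 0 = 0% [clear], 1 = >0% to <10" and so on upward.

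The same section then deals with incomplete records:

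- **One or two regions.** The trigger is a missing area and/or a missing set of three severity ratings. When "all severity measurements for up to 2 regions are missing, then the missing (R+T+S) x A for a region will be substituted by the average", with that average taken over the regions whose product is known.
- **More than two regions, whole body clear.** If the same information is lacking "but the BSA (Body Surface Area) is reported as 0 for the study participant, then the overall PASI score will be set to 0".
- **More than two regions, any other case.** "Otherwise, the PASI will be set to missing".

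The whole-body rule came in with SAP Amendment 2. The change log in SAP 6.4.1 records it as "Revised derivation to set overall PASI score to 0 when BSA is 0 and the participant is missing area and/or severity measurements" for more than two regions.

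SAP 5.1.1.7.3 makes a missing binary efficacy response a nonresponse in the main analysis. SAP 5.4.1.3 names the observed-case (OC) analysis as the sensitivity check.

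**The concern.** The trigger is joined by and/or, so it covers a region whose area is recorded but whose three severity items are blank. Where that area is 0, nothing is unknown, because (R+T+S) x 0 = 0 whatever R, T and S would have been. The literal rule replaces this known zero with the mean of regions that may still be diseased. If more than two regions are in this state and total BSA is above 0, it discards the score altogether.

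The rule for BSA 0 applies the right principle to the whole body but not to a single region. It leaves out participants with one or two regions still involved, and many PASI90 calls are decided among them.

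At stake are PASI90 at Week 16 and PASI75 at Week 4 (both secondary), the PASI responses over time, the absolute PASI thresholds (SAP 5.5.1), PASI change (SAP 5.5.2), and any exposure-response work that uses the same derived score.

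**Working it through.** **Inputs.** Weights, scales and missing-item rules: SAP 6.1.6.1. Nonresponder imputation: SAP 5.1.1.7.3. At least 20 participants per dose group: SAP 1.2. Baseline PASI of at least 12, or at least 10 with specified involvement: Protocol 5.1. Assumption, not in the documents: the severity items of some clear regions are blank.

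**Check of the formula.** Maximum PASI = (0.1 + 0.2 + 0.3 + 0.4) x 12 x 6 = 72, as SAP 6.1.6.1 states.

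Products below are in the order head, upper, trunk, lower.

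**1. Inflation that loses PASI90.** Baseline 16, products (0, 0, 2, 2), head and upper blank.
- True PASI = 0.3 x 2 + 0.4 x 2 = 1.4. Improvement = (16 - 1.4)/16 = 91.3%: responder.
- Rule: mean of available products = (2 + 2)/2 = 2. PASI = (0.1 + 0.2 + 0.3 + 0.4) x 2 = 2.0. Improvement = 87.5%: nonresponder.

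**2. Set to missing.** Baseline 16, products (0, 0, 0, 3), three clear regions blank, BSA above 0.
- True PASI = 0.4 x 3 = 1.2. Improvement = 92.5%: responder.
- Rule: missing, hence nonresponder.

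**3. PASI75 can be affected too.** Baseline 16, products (0, 0, 6, 5), head and upper blank.
- True PASI = 0.3 x 6 + 0.4 x 5 = 3.8. Improvement = 76.3%: responder.
- Rule: mean = 5.5. PASI = 3.8 + 0.3 x 5.5 = 5.45. Improvement = 65.9%: nonresponder.

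**4. Not every case flips.** Baseline 12, products (0, 0, 0, 2), true PASI 0.8 (93.3%). Two clear regions are blank and the third is scored 0, so the mean of available products is (0 + 2)/2 = 1.
- Head and upper blank: 0.8 + 0.1 + 0.2 = 1.1 (90.8%), still a responder.
- Upper and trunk blank: 0.8 + 0.2 + 0.3 = 1.3 (89.2%), nonresponder.

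**5. Fully clear skin.** All four products 0 and BSA 0. With one or two regions blank the available products average 0. With three or four blank the BSA rule applies. All 16 blank patterns return PASI 0.

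**6. Baseline.** Products (0, 12, 18, 18), head clear and blank.
- True Baseline PASI = 2.4 + 5.4 + 7.2 = 15.0.
- Rule: mean = 48/3 = 16. PASI = 15.0 + 0.1 x 16 = 16.6.
- The PASI90 cut-off (10% of Baseline) rises from 1.50 to 1.66, which makes response easier.

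**7. How many score patterns are exposed.** All combinations of products 0 to 3 were enumerated, with at least one clear region and at least one involved, keeping those that are truly PASI90. With every clear region blank:

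| Baseline PASI | Truly PASI90 | Lost by inflation | Lost as missing | Total lost |
|---|---|---|---|---|
| 12 | 85 | 61 | 12 | 73 |
| 16 | 131 | 77 | 12 | 89 |
| 20 | 160 | 61 | 12 | 73 |

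With only one clear region blank and the others scored 0, counting each choice of blank region separately, the loss is 64 of 205 (31%) at Baseline 16 and 44 of 237 (19%) at Baseline 20. These are counts of equally weighted patterns, not probabilities.

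**8. Weight of one participant.** 1/20 = 5 percentage points. For example, 16/20 = 80% (Clopper-Pearson 95% CI 56.3 to 94.3) becomes 15/20 = 75% (50.9 to 91.3).

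**The case against.** The strongest reply is that the trigger may never arise. The severity scale has its own zero (Protocol 8.1.1: "0=none, 1=slight, 2=moderate, 3=marked, and 4=very marked"), and the Investigator is to rate every body area, with no instruction to skip clear ones. A clear region scored 0/0/0 has product 0 and nothing is missing. The documents do not show how the eCRF treats severity fields when area is 0. This stands: the effect is conditional.

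The Amendment 2 rule might be taken as proof that blanks occur. It is not. It suggests that blanks in clear participants were foreseen, but it fits a largely uncompleted form with BSA 0 equally well, and it says nothing direct about single blank regions beside residual disease.

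A programmer could also hold that a product with A = 0 is known, hence not missing, and code the one-or-two-region rule correctly. The wording allows that. It allows it less clearly for the sentence on more than two regions, and a secondary endpoint should not depend on which reading is chosen.

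Finally, plasma concentration is the primary endpoint, efficacy is descriptive without testing, and IGA 0/1 is untouched. All true, and they limit the consequence. The OC analysis gives only partial cover: it drops a missing PASI, but an inflated PASI counts as observed. The PK-PPS repeat uses the same derived score. The absolute PASI counts are OC only, so missing scores drop out of them while inflated ones stay.

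**Conclusion.** The gap in the text is real: SAP 6.1.6.1 has no exception for A = 0, and the literal rule can give a wrong PASI and a wrong PASI90 or PASI75 call in some participants with residual disease. The size is about 5 percentage points of PASI90 per misclassified participant, assuming about 20 per arm and severities left blank in clear regions. If severities are always recorded, the effect is nil.

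Four stronger conclusions are tempting and are not supported:

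- *False PASI100 nonresponders.* Fully clear participants with BSA 0 still score 0 (step 5), and anyone with residual disease is not a true PASI100 responder.
- *A bias in one direction.* Post-Baseline inflation lowers response, but a blank clear region at Baseline raises it (step 6). The net direction is not determined.
- *A penalty on the dose group that clears more.* This would need a known net direction and the frequency of blanks by arm. Neither is available.
- *A loss of 68% of PASI90 responders.* That figure (89/131) counts patterns on an arbitrary grid with every clear region blank.

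**What to change.** In SAP 6.1.6.1, before the substitution rules, add: *If the area score A for a region is 0, (R+T+S) x A for that region is 0, whether or not severity items are recorded, and the region counts as available.* Then confine the averaging and set-to-missing rules to regions with A missing, or with A above 0 and all severity items missing.

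Confirm how the eCRF handles the severity fields when area is 0, and count the records with A = 0 and all severities blank, separately at Baseline and after it. If there are none, the added sentence is a clarification only.

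The cost is one sentence and one line of derivation code. No new data are needed, and fully recorded scores do not change.

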6.1.6.2 Exposure-adjusted rates

The EAIR is defined as the number of participants (n) with a specific AE adjusted for the exposure and will be scaled to 100 participant-years:

$$EAIR = 100 \times n / \sum_{i=1}^N (T_{Risk(i)})$$

Where $T_{Exp(i)}$ is the exposure time for the i^{th} participant and N is the number of participants at risk.

If a participant has multiple events, the time of exposure is calculated to the first occurrence of the AE being considered. If a participant has no events, the total time at risk is used.

Exact Poisson 95% confidence intervals for incidence rates are calculated using the relationship between the Poisson and the Chi-square distribution (Ulm, 1990; Fay and Feuer, 1997):

$$LCL = \frac{\chi_{2n, \alpha/2}^2}{2 \times \sum_{i=1}^n (T_{Exp(i)})}$$

$$UCL = \frac{\chi_{2(n+1), 1-\alpha/2}^2}{2 \times \sum_{i=1}^n (T_{Exp(i)})}$$

where n is the number of participants with a specific AE for the incidence rate of interest and is the basis for the number of the degrees of freedom for the chi-square quantile for the upper tail probability χ^2 .

The EAER will be the number of AEs including repeat occurrences in individual participants divided by the total time at risk scaled to 100 participant-years and calculated using:

$$EAER = 100 \times N_{AE} / \sum_{i=1}^N (T_{Risk(i)})$$

where N_{AE} is the total number of AEs, $T_{Risk(i)}$ is the time at risk for then i^{th} participant, and N is the total number of participants at risk.

No confidence interval will be computed for EAER.

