5.6.2.1 General data considerations for AEs

Treatment-emergent AEs are defined as those AEs that have a start date on or following the first dose of IMP through the final dose of study treatment +20 weeks (140 days).

The rules for imputing partial start or stop dates are outlined in Section 5.14.7.5. If it is not possible (due to partial dates) to determine whether an AE is treatment-emergent then it will be assumed to be a TEAE. If the intensity of an AE is unknown, it will be considered as severe. If the relationship to study drug is missing, it will be considered as related.

Treatment-emergent AEs will be summarized as participant incidence (number and percentage of participants experiencing the AE) and AE frequencies (number of AEs including repeat events) by weight-categorized dose group for the Initial Treatment Period, OLE Period, and the combined periods. Treatment-emergent AEs will be attributed to Initial Treatment Period and OLE Period based on duration of exposure definition in Section 5.6.1. For AEs that emerged after 140 days of first dosing but still within the 140 days after last dose window, those AEs will be classified as TEAE but will be excluded from the output based on the Initial Treatment Period. However, these AEs will be included in the AE summaries for Initial Treatment Period and OLE Treatment Period combined.

For AEs that emerged > 140 days after the last dose, these AEs will only be listed in an “All Adverse Events” listing and will not be summarized.

Selected AE summaries will include the exposure-adjusted incidence rate (EAIR) and the exposure-adjusted event rate (EAER). The 95% CIs will be reported for the EAIR only.

The EAIR is the total number of participants with a specific AE divided by the total time at risk across all participants. If a participant has multiple events, the time of exposure is calculated to the first occurrence of the AE being considered with respect to the period being summarized. If a participant has no events, the total time at risk is used. The EAER is the total number of AEs including repeat occurrences in individual participants divided by the total time at risk across all participants with respect to the period being summarized. Exposure adjusted rates (EAIR and EAER) will be scaled to 100 participant-years. Participant time at risk represents the time a participant is at risk for having an AE. These definitions will be used in calculations of exposure-adjusted rates for adverse events.

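### The printed 95% limits for the exposure-adjusted incidence rate sum person-time only over participants with the event and omit the factor 100, so they do not match the rate they accompany

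*SAP*

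**What the plan says.** SAP 6.1.6.2 gives the EAIR as 100 × n divided by the sum of T_Risk(i) for i = 1 to N, where "N is the number of participants at risk". SAP 5.6.2.1 puts the same thing in words: "The EAIR is the total number of participants with a specific AE divided by the total time at risk across all participants". It adds that the rates are scaled to 100 participant-years, and SAP 5.6.1 expresses time at risk in years.

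The confidence limits in 6.1.6.2 are meant to be exact Poisson limits obtained from chi-square quantiles. As printed:

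- LCL = χ²(2n; α/2) / (2 × sum of T_Exp(i) for i = 1 to n)
- UCL = χ²(2(n+1); 1−α/2) / (2 × sum of T_Exp(i) for i = 1 to n)

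The sentence after them reads "where n is the number of participants with a specific AE for the incidence rate of interest" and describes the quantile as "the chi-square quantile for the upper tail probability". On which rates get an interval, SAP 5.6.2.1 says: "The 95% CIs will be reported for the EAIR only".

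The change log in SAP 6.4.1 records that the LCL and UCL formula was corrected in this amendment, so the printed version is the one in force.

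**The concern.** The rate and its limits should share one denominator and one scale. Here they share neither: the rate divides by everyone's person-time and is multiplied by 100, while the limits divide by the person-time of those with the event and are not.

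These are the only intervals planned for the adverse event rates. They are attached to the exposure-adjusted safety topics of interest, which are a named secondary endpoint (SAP Table 1–1). They also belong to the tables of any TEAE, serious TEAEs, and TEAEs leading to withdrawal from the study or discontinuation of IMP (SAP 5.6.2.2). With about 20 participants per dose group, split further by weight category, the width of the interval is the reader's main protection against over-reading a rate. Zero counts are likely for rare topics such as TB or IBD, and there the printed formula gives no upper limit at all.

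**Working it through.** The SAP contains no numerical EAIR or interval, so there is no stated figure to reproduce. The check applies the printed formulas to an illustration.

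**Inputs from the documents**
- 20 participants per dose group (SAP 1.2 and 3).
- 140 days in the Initial Treatment Period (SAP 5.6.1.1).
- Years = days / 365.25 (SAP 5.6.1).
- α = 0.05, two-sided.

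**Assumed inputs (not in the documents)**
- The number of participants with an event and the day of first event. The main case is 3 of 20, each at day 70.

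**Main case**
- Person-time over all N: (17 × 140 + 3 × 70) / 365.25 = 2590 / 365.25 = 7.091 years.
- Person-time over the n with an event: 3 × 70 / 365.25 = 0.575 years.
- EAIR = 100 × 3 / 7.091 = 42.3 per 100 participant-years.
- Quantiles: χ²(0.025; 6) = 1.237 and χ²(0.975; 8) = 17.53.

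| Version | Lower | Upper | Contains 42.3? |
|---|---|---|---|
| As printed | 1.237 / (2 × 0.575) = 1.08 | 17.53 / (2 × 0.575) = 15.2 | No |
| Factor 100 added, sum still to n | 107.6 | 1524.9 | No |
| Sum corrected to N, no factor 100 | 0.09 | 1.24 | No |
| Both corrected | 100 × 1.237 / (2 × 7.091) = 8.7 | 100 × 17.53 / (2 × 7.091) = 123.6 | Yes |

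**Why the result varies.** Write T_N and T_n for the two person-time sums. Each printed limit equals the correct limit × (T_N / T_n) / 100. In the main case the multiplier is (2590 / 210) / 100 = 0.123, so 123.6 becomes 15.2. The short sum pushes the limits up and the missing 100 pushes them down. They cancel only if T_N happens to be 100 times T_n.

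| Scenario (140 days) | EAIR | Printed CI | Correct CI | Printed CI contains the rate? |
|---|---|---|---|---|
| 1 of 20, day 70 | 13.4 | 0.13 to 29.1 | 0.34 to 74.5 | Yes |
| 10 of 20, day 70 | 173.9 | 2.50 to 9.60 | 83.4 to 319.9 | No, too low |
| 3 of 40, at 10% of follow-up | 21.0 | 5.38 to 76.2 | 4.33 to 61.3 | Yes |
| 3 of 40, at 2% of follow-up | 21.1 | 26.9 to 381 | 4.36 to 61.7 | No, too high |

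**No events.** With n = 0 the printed sum is empty and the upper limit divides by zero. The corrected form gives T_N = 20 × 140 / 365.25 = 7.67 years and an interval of 0 to 48.1 per 100 participant-years.

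**If only the sum is corrected.** With person-time over N but no factor 100, UCL / EAIR = χ²(0.975; 2(n+1)) / (200n). At n = 1 this is 11.14 / 200 = 0.056, and it falls as n rises. The interval then lies below the rate for every n ≥ 1, whatever the person-time.

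**The case against.** The best defence is that the intention is clear. The exact Poisson method is named, 5.6.2.1 states the denominator and scale in words, and Protocol 9.4.1.1 promises rates per 100 patient-years with 95% CIs. The rule in 6.1.6.2 for participants with no event only makes sense if they are in the sum. A competent programmer might therefore put it right unprompted. All of this supports calling it a specification error rather than a wrong method. It does not make the printed formula correct, and a formula logged as just corrected is likely to be trusted.

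The lower-case n might be an artefact of reading the PDF. That is unlikely, since both limits show n while the EAIR and EAER sums show N. Granting it leaves the missing factor 100, which alone is enough to exclude the rate whenever n ≥ 1. The limits might be meant for an unscaled rate, but the SAP defines none, and that would not repair the sum.

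Three stronger readings are tempting and are not supported:

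- *The limits use a different time variable.* The line defining T_Exp stands directly under a formula printed with T_Risk, and the next lines describe time censored at the first event, or total time at risk if there is none. This is two symbols for one quantity, not the dosing-duration exposure of SAP 5.6.1.
- *The upper-tail wording swaps the limits.* The α/2 and 1−α/2 pair with 2n and 2(n+1) degrees of freedom is the standard one. Taken literally, the phrase would put the lower limit above the upper (101.9 and 15.4 in the main case, even with sum and scale corrected), so it is loose wording.
- *The interval always excludes its rate.* The second table shows otherwise; it depends on how many participants have events and when.

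**Conclusion.** The two limit formulas in SAP 6.1.6.2 are wrong as written in two respects: the person-time sum stops at n instead of N, and the factor 100 is missing. Both contradict SAP 5.6.2.1. In the main case the upper limit is understated about eightfold (15.2 against 123.6) and the rate of 42.3 lies outside its interval. In other cases the printed interval contains the rate but is still wrong, and with no events it cannot be computed.

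The sizes rest on assumed event counts and timings, with 20 or 40 participants and 140 days of follow-up. The formula fault itself rests on no assumption beyond the printed text.

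This is a should-fix correction. All analyses are descriptive (SAP 2), the primary endpoint is plasma concentration, and no stopping rule in the SAP depends on these limits. It nevertheless affects every interval reported for the exposure-adjusted safety secondary endpoint.

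**What to change.** Replace the two limits in SAP 6.1.6.2 by:

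- LCL = 100 × χ²(α/2; 2n) / (2 × sum over i = 1 to N of T_Risk(i)), with LCL = 0 when n = 0
- UCL = 100 × χ²(1−α/2; 2(n+1)) / (2 × sum over i = 1 to N of T_Risk(i))

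Here T_Risk(i) is the same first-event-censored time, in years, that forms the EAIR denominator.

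As tidy-up only, use one symbol in place of T_Exp and T_Risk, and describe the quantiles as lower-tail (cumulative).

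The cost is one formula in the SAP and one check of the program that produces the limits. The main case above (8.7 to 123.6 around 42.3) and the n = 0 case (0 to 48.1) can serve as test values. No data collection or design feature changes.
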